## 8 Visit schedule and assessments

The Assessment Schedule ([Table 8-1](#)) lists the assessments when they are performed. All data obtained from these assessments must be supported in the participant’s source documentation.

Participants should be seen for all visits/assessments as outlined in the assessment schedule ([Table 8-1](#)) or as close to the designated day/time as possible (+/- 7 days). Missed or rescheduled visits should not lead to automatic discontinuation. Participants may be seen at

any time for an unscheduled visit, e.g., if they experience deterioration or AEs that in the opinion of the Investigator/qualified site staff requires closer monitoring.

Participants who discontinue from study treatment should continue to attend the remaining study visits as indicated in the Assessment Schedule ([Table 8-1](#)).

Participants who discontinue from study or withdraw their consent should be scheduled for a final evaluation visit if they agree, as soon as possible, at which time all of the assessments listed for the final visit will be performed. At this final visit, all investigational product should be reconciled, and the adverse event and concomitant medications not previously reported must be recorded on the eCRF.

Participants will have to comply with the following restrictions during the study:

- Participants need to fast for at least 8 hours for all visits (measurement of lipids/lipoproteins and blood glucose requires participants to be fasting). If the participant has not fasted, the collection of laboratory evaluations must be rescheduled.
- Blood donation will not be allowed at any time during the study

The “X” in the table denotes the assessments to be recorded in the clinical database or received electronically from a vendor. The “S” in the table denotes the assessments that are only in the participant’s source documentation and do not need to be recorded in the clinical database.

As per [Section 4.6](#), during a Public Health Emergency that limits or prevents on-site study visits, alternative methods of providing continuing care may be implemented by the Investigator as the situation dictates. If allowable by a local Health Authority and depending on operational capabilities, phone calls, virtual contacts (e.g. tele consult) or visits by site staff/ home nursing staff to the participant’s home, can replace on-site study visits, for the duration of the disruption until it is safe for the participant to visit the site again.

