## **9 Study discontinuation and completion**

### **9.1 Discontinuation and completion**

#### **9.1.1 Study treatment discontinuation and study discontinuation**

Discontinuation of study treatment for a participant occurs when study treatment is stopped earlier than the protocol planned duration and can be initiated by either the participant or the investigator.

The investigator must discontinue study treatment for a given participant if, he/she believes that continuation would negatively impact the participant's well-being.

Study treatment must be discontinued under the following circumstances:

- Participant/guardian decision
- Pregnancy
- Use of prohibited treatment as per recommendations in the prohibited treatment section
- Any situation in which study participation might result in a safety risk to the participant
- Any severe suspected drug related AE at the investigator's discretion

If discontinuation of study treatment occurs, the investigator should make a reasonable effort to understand the primary reason for the participant's premature discontinuation of study treatment and record this information.

Participants who discontinue study treatment or who decide they do not wish to participate in the study further should NOT be considered withdrawn from the study UNLESS they withdraw their consent (see 'Withdrawal of Informed Consent' section). **Where possible, they should return for the assessments indicated** in the Assessment Schedule. If they fail to return for these assessments for unknown reasons, every effort (e.g. telephone, e-mail, letter) should be made to contact the participant/pre-designated contact as specified in the lost to follow-up section. This contact should preferably be done according to the study visit schedule. Unless a participant withdraws informed consent, personal and coded data are able to be collected in accordance with the informed consent form.

If the participant cannot or is unwilling to attend any visit(s), the site staff should maintain regular telephone contact with the participant, or with a person pre-designated by the participant. This telephone contact should preferably be done according to the study visit schedule.

After study treatment discontinuation, at a minimum, in abbreviated visits, the following data should be collected at clinic visits or via telephone/email contact:

- New / concomitant treatments
- Adverse Events / Serious Adverse Events

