### **12.4.2 Statistical model, hypothesis, and method of analysis**

The primary analysis of primary efficacy variable 1 to address the primary objective will be based on the following estimand:

- Population: Defined through appropriate inclusion/exclusion criteria to reflect the targeted population
- Variable: Percent change from baseline in LDL-C [The primary analysis time point is at Day 330.]
- Treatment: "Inclisiran first" implementation strategy or usual care
- Remaining intercurrent events: 1. Potential use of inclisiran by participants in the usual care group. This intercurrent event will be ignored in the analysis, as the design of the trial allows for participants in the usual care group to potentially use inclisiran. 2. Discontinuation of study treatment. This intercurrent event will be ignored in the analysis.
- Summary measure: Least-squares mean difference between "inclisiran first" implementation strategy and usual care

The null hypothesis is that the mean percent change from baseline in LDL-C at Day 330 for "inclisiran first" implementation strategy and usual care groups are equal. The alternative hypothesis is that the mean percent change from baseline in LDL-C at Day 330 for "inclisiran first" implementation strategy group is not equal to that of the usual care group.

Primary efficacy variable 1 will be analyzed using mixed-effects model repeated measures (MMRM) with treatment, visit, baseline, [REDACTED], treatment-by-visit interaction, and baseline-by-visit interaction as explanatory variables. An unstructured working correlation matrix will be assumed for this model (Diggle et al 2002). Least-squares mean of each treatment group, least-squares mean treatment difference, two-sided 97.5% confidence interval for the treatment difference, and p-value based on the fitted MMRM will be reported for each applicable visit (day). If the p-value based on a two-sided test for treatment effect at Day 330 is  $< 0.025$  and the corresponding least squares mean treatment difference ("inclisiran first" implementation strategy – usual care) is less than 0, statistical significance in favor of "inclisiran first" implementation strategy is shown. All efforts will be made to follow up participants until the end of the study. Participants will be expected to follow the visit schedule and assessments even after discontinuation of study treatment. Data after participants discontinued study treatment will be used in the analysis ("retrieved dropout").

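### The fallback data list after treatment discontinuation omits LDL-C even at clinic visits, although the primary LDL-C estimand relies on values collected after discontinuation

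*Protocol*

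**What the plan says.** **The default is full follow-up.** Protocol Section 8: "Participants who discontinue from study treatment should continue to attend the remaining study visits as indicated in the Assessment Schedule". Table 8-1 schedules lipids at every visit. Section 9.1.1 repeats the default with a qualifier: "Where possible, they should return for the assessments indicated". Section 12.4.2 also expects the schedule to be followed after discontinuation.

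**The fallback is in the same Section 9.1.1.** After a paragraph on participants who cannot or will not attend, it says: "After study treatment discontinuation, at a minimum, in abbreviated visits, the following data should be collected", and it names clinic visits as well as telephone or email as the setting. Two items follow: "New / concomitant treatments" and "Adverse Events / Serious Adverse Events". No blood sample is listed.

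**The analysis needs the later values.** Primary estimand 1 (Protocol 2.1, SAP 1.2.1) ignores discontinuation of study treatment. For the primary MMRM, Protocol 12.4.2 says: "Data after participants discontinued study treatment will be used in the analysis"; SAP 2.5.2 has the same rule. Missing LDL-C is handled as missing at random (Protocol 12.4.4, SAP 2.5.4).

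**The concern.** The fallback list serves one primary variable and not the other. Concomitant treatments, which determine statin discontinuation, are on it. LDL-C is not, although the sentence expressly covers clinic visits, where blood could be drawn. A coordinator who works from this list during an abbreviated clinic visit has no prompt to take the sample.

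Three features make the gap worth closing.

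- It falls almost entirely on one arm. SAP 1.2.1 and 2.5.3 place this intercurrent event in inclisiran participants, and usual care receives no study drug. If a lost effect goes unmeasured, the error favours the inclisiran-first strategy.
- It blurs two estimands. The supplementary analysis (Protocol 12.4.6, SAP 2.5.6) deliberately drops data after discontinuation. For a discontinuer with no later LDL-C, the primary and supplementary analyses use the same data.
- No planned sensitivity analysis would show it. Protocol 12.4.5 and SAP 2.5.5 give a rank-based analysis and an exclusion of participants whose randomization-system and CRF entries disagree. Neither tests departures from missing at random.

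**Working it through.** **The plan's own figure.** Inputs from Protocol 12.8.1: difference 15, SD 40, two-sided alpha 0.025, power 0.90.

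n per arm = 2 × (2.2414 + 1.2816)² × 40² / 15² = 176.5, rounded up to 177, so 354 in total. This matches Table 12-1. Inflation for the stated 20%: 177 / 0.8 = 221.25, rounded up to 222 per arm, 444 in total. Both figures reproduce, and the fix changes neither.

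**Precision is not the issue.** With 222 per arm randomized and the same inputs, LDL-C power is 95.6% with nothing missing, 93.4% with 10% missing and 90.2% with 20% missing.

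**Bias against the estimand.** The documents do not give the share of participants who stop treatment and have no later LDL-C, so these inputs are assumptions:

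- on-treatment difference from usual care: 15 points, the planning value;
- d: share of the inclisiran-first arm that stops treatment and has no later LDL-C, 2% to 20%;
- D_off: those participants' true difference from usual care at Day 330, 0 to 10 points, with 15 meaning full persistence;
- the model fills them in at the on-treatment level.

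True treatment-policy difference = (1 − d) × 15 + d × D_off.

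Overstatement = 15 − that value = d × (15 − D_off).

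| d | D_off = 0 | D_off = 5 | D_off = 10 | D_off = 15 |
|---|---|---|---|---|
| 2% | 0.30 | 0.20 | 0.10 | 0 |
| 5% | 0.75 | 0.50 | 0.25 | 0 |
| 10% | 1.50 | 1.00 | 0.50 | 0 |
| 20% | 3.00 | 2.00 | 1.00 | 0 |

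If other discontinuers do supply later values, these pull the filled-in mean towards D_off, and the overstatement is somewhat smaller.

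**Scale.** On the planning values the standard error of the difference is 40 × √(2/177) = 4.25 points. An overstatement of 0.75 is 0.75 / 4.25 = 0.18 standard errors; the extreme of 3.0 is 0.71.

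**The case against.** The strongest reply is that full follow-up is stated repeatedly and the two-item list is only a floor. The protocol glossary defines discontinuation from study treatment as a state in which the participant agrees to the other required assessments. A site that skips the draw for a willing attendee departs from Section 8. This stands. A reader might infer that LDL-C collection ends when treatment stops, or that a site can follow the whole protocol and still leave Day 330 LDL-C unmeasured in someone willing to attend. The documents support neither reading. What remains is a mismatch between the default and the fallback's wording for clinic visits.

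Second, telephone and email contacts cannot yield LDL-C whatever the list says. This also stands. The gain is limited to abbreviated clinic visits and feasible remote draws.

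Third, there are mitigations. Participants who leave the study are offered a final visit with all final-visit assessments (Section 8). The Day 330 window is wide and accepts unscheduled visits (SAP 2.1.1). EHR and claims lipid values complement site data (Section 3). These help in part, but no rule says how an EHR value would enter the Day 330 analysis.

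Fourth, the size is assumed, and full loss of effect is a worst case. Section 1.1.5 describes sustained lowering with twice-yearly injections, and someone who stops after Day 270 has already had all three planned doses. A reader might also apply the reduction of 50% or more seen against placebo (Section 1.1), which at a 5% share would give 0.05 × 50 = 2.5 points. That is not the comparison planned here; Section 12.8.1 assumes 15 against usual care.

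**Conclusion.** The concern holds in a narrow form. The default after treatment discontinuation is complete, but the Section 9.1.1 minimum for abbreviated visits leaves out the one sample that primary variable 1 needs, even when the participant is in the clinic.

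The plausible bias is small: about 0.1 to 3.0 points on a planned 15, resting on an assumed 2% to 20% share without later LDL-C and an assumed true difference of 0 to 10 points in that share. It disappears if the effect persists. It is unlikely to change the superiority conclusion; what it affects is the accuracy of the estimate under the stated estimand. Primary variable 2 is less exposed, because concomitant treatments are on the list. This is a cheap improvement, not a flaw that undermines the trial.

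**What to change.** 1. Add to the Section 9.1.1 minimum list a fasting lipid sample at any abbreviated clinic visit, with priority for the Day 330 window (study days 301 to 375 in SAP Table 2-2). SAP 2.1.1 already accepts scheduled and unscheduled values in the window, so no new analysis rule is needed.
2. State that the procedures under Remote procedures in Section 3 may be used for discontinuers at sites that already offer them. This has to be explicit: the home-draw text elsewhere in Section 3 and in Table 8-1, footnote 1, is tied to a Public Health Emergency, and remote procedures are offered only at sites chosen by the sponsor.

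Cost: a short amendment to wording, for a sample already scheduled in Table 8-1. The downside is some effort to obtain draws from reluctant participants, with no gain for those reached only by telephone or email.

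If follow-up is already complete, the collection change comes too late. The report can still give, by arm, the number of discontinuers without Day 330 LDL-C and add a sensitivity analysis for departures from missing at random.

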### 9.1.2 Withdrawal of informed consent

Participants may voluntarily withdraw consent to participate in the study for any reason at any time. Withdrawal of consent occurs only when a participant:

- Does not want to participate in the study anymore,

and

- Does not want any further study related contacts

In this situation, the investigator should make a reasonable effort (e.g. telephone, e-mail, letter) to understand the primary reason for the participant's decision to withdraw his/her consent and record this information.

Study treatment must be discontinued and no further assessments conducted, and the data that would have been collected at subsequent visits will be considered missing.

Further attempts to contact the participant are not allowed unless safety findings require communicating or follow-up.

All efforts should be made to complete the assessments prior to study discontinuation. A final evaluation at the time of the participant's study discontinuation should be made as detailed in the assessment table.

Novartis will continue to retain and use all research results (data) that have already been collected for the study evaluation.

### **9.1.3 Lost to follow-up**

For participants whose status is unclear because they fail to appear for study visits without stating an intention to discontinue or withdraw, the investigator must show "due diligence" by documenting in the source documents steps taken to contact the participant, e.g. dates of telephone calls, registered letters, etc. A participant should not be considered as lost to follow-up until due diligence has been completed or until the end of the study.

### **9.1.4 Early study termination by the sponsor**

The study can be terminated by Novartis at any time.

Reasons for early termination:

- Unexpected, significant, or unacceptable safety risk to participants enrolled in the study
- Decision based on recommendations from applicable board(s) after review of safety and efficacy data
- Discontinuation of study drug development

In taking the decision to terminate, Novartis will always consider participant welfare and safety. Should early termination be necessary, participants must be seen as soon as possible and treated as a prematurely withdrawn participant. The investigator may be informed of additional procedures to be followed in order to ensure that adequate consideration is given to the protection of the participant's interests. The investigator or sponsor depending on local regulation will be responsible for informing IRBs/IECs of the early termination of the trial.

## **9.2 Study completion and post-study treatment**

At the study completion/end of study visit, including participants who are prematurely withdrawn from the study, the referring or primary physician will continue to provide ongoing medical care. When the participant has completed all scheduled study assessments, the investigator must call the IRT to record the participant completion in the IRT.

Study completion is defined as when the last participant finishes their Study Completion Visit and any repeat assessments associated with this visit have been documented and followed-up appropriately by the Investigator or, in the event of an early study termination decision, the date of that decision (e.g. Each participant will be required to complete the study in its entirety and thereafter no further study treatment will be made available to them).

For study participants who have successfully completed the study/treatment epoch, further guidance will be provided separately concerning continuation of treatment and access to investigational drug. This guidance will be provided to sites prior to the completion visit of the first patient (first patient last visit). For study participants who terminate prior to the end of the treatment epoch or who withdraw from treatment, continuing treatment should be managed by the investigator and/or referring physician.

## **10 Safety monitoring and reporting**

### **10.1 Definition of adverse events and reporting requirements**

#### **10.1.1 Adverse events**

An adverse event (AE) is any untoward medical occurrence (e.g. any unfavorable and unintended sign [including abnormal laboratory findings], symptom or disease) in a clinical investigation participant after providing written informed consent for participation in the study. Therefore, an AE may or may not be temporally or causally associated with the use of a medicinal (investigational) product.

The investigator has the responsibility for managing the safety of individual participant and identifying adverse events.

Novartis qualified medical personnel will be readily available to advise on trial related medical questions or problems.

The occurrence of adverse events must be sought by non-directive questioning of the participant at each visit during the study. Adverse events also may be detected when they are volunteered by the participant during or between visits or through physical examination findings, laboratory test findings, or other assessments.

Adverse events must be recorded under the signs, symptoms, or diagnosis associated with them, accompanied by the following information (as far as possible) (if the event is serious refer to [Section 10.1.2](#)):

1. The severity grade:
  - mild: usually transient in nature and generally not interfering with normal activities
  - moderate: sufficiently discomforting to interfere with normal activities
  - severe: prevents normal activities
2. Its relationship to the study treatment. If the event is due to lack of efficacy or progression of underlying illness (i.e. progression of the study indication) the assessment of causality will usually be 'Not suspected.' The rationale for this guidance is that the symptoms of a lack of efficacy or progression of underlying illness are not caused by the trial drug, they happen in spite of its administration and/or both lack of efficacy and progression of underlying disease can only be evaluated meaningfully by an analysis of cohorts, not on a single participant.
3. Its duration (start and end dates) or if the event is ongoing, an outcome of not recovered/not resolved must be reported.

4. Whether it constitutes a SAE (see [Section 10.1.2](#) for definition of SAE) and which seriousness criteria have been met.
5. Action taken regarding study treatment.

All adverse events must be treated appropriately. Treatment may include one or more of the following:

- Dose not changed
  - Dose Reduced/increased
  - Drug interrupted/withdrawn
6. Its outcome (i.e. recovery status or whether it was fatal)

Conditions that were already present at the time of informed consent should be recorded in medical history of the participant.

Adverse events (including lab abnormalities that constitute AEs) should be described using a diagnosis whenever possible, rather than individual underlying signs and symptoms.

Adverse event monitoring should be continued for at least 30 days following the last dose of study treatment.

Once an adverse event is detected, it must be followed until its resolution or until it is judged to be permanent (e.g. continuing at the end of the study), and assessment must be made at each visit (or more frequently, if necessary) of any changes in severity, the suspected relationship to the interventions required to treat it, and the outcome.

Information about adverse drug reactions for the investigational drug can be found in the Investigator's Brochure.

Abnormal laboratory values or test results constitute adverse events only if they fulfill at least one of the following criteria:

- they induce clinical signs or symptoms
- they are considered clinically significant
- they require therapy

Clinically significant abnormal laboratory values or test results must be identified through a review of values outside of reference ranges/clinically notable ranges, significant changes from baseline or the previous visit, or values which are considered to be non-typical in participant with the underlying disease. Alert ranges for laboratory and other test abnormalities are included in [Appendix 1](#).

### **10.1.2 Serious adverse events**

An SAE is defined as any adverse event [appearance of (or worsening of any pre-existing)] undesirable sign(s), symptom(s), or medical condition(s) which meets any one of the following criteria:

- fatal
- life-threatening

Life-threatening in the context of a SAE refers to a reaction in which the participant was at risk of death at the time of the reaction; it does not refer to a reaction that hypothetically might have caused death if it were more severe (please refer to the ICH-E2D Guidelines).

- results in persistent or significant disability/incapacity
- constitutes a congenital anomaly/birth defect
- requires inpatient hospitalization or prolongation of existing hospitalization, unless hospitalization is for:
  - routine treatment or monitoring of the studied indication, not associated with any deterioration in condition
  - elective or pre-planned treatment for a pre-existing condition that is unrelated to the indication under study and has not worsened since signing the informed consent
  - social reasons and respite care in the absence of any deterioration in the participant's general condition
  - treatment on an emergency outpatient basis for an event not fulfilling any of the definitions of a SAE given above and not resulting in hospital admission
- is medically significant, e.g. defined as an event that jeopardizes the participant or may require medical or surgical intervention to prevent one of the outcomes listed above

Medical and scientific judgment should be exercised in deciding whether other situations should be considered serious reactions, such as important medical events that might not be immediately life threatening or result in death or hospitalization but might jeopardize the participant or might require intervention to prevent one of the other outcomes listed above. Such events should be considered as “medically significant.” Examples of such events are intensive treatment in an emergency room or at home for allergic bronchospasm, blood dyscrasias, or convulsions that do not result in hospitalization or development of dependency or abuse (please refer to the ICH-E2D Guidelines).

All new malignant neoplasms will be assessed as serious under “medically significant” if other seriousness criteria are not met and the malignant neoplasm is not a disease progression of the study indication.

Any suspected transmission via a medicinal product of an infectious agent is also considered a serious adverse reaction.

All reports of intentional misuse and abuse of the product are also considered serious adverse event irrespective if a clinical event has occurred.

